11.1.4. Definition of Relationship to Study Drug

The Principal Investigator or medically qualified designee must review each AE and make the determination of relationship to study drug using the following guidelines:

Not Related: The event can be readily explained by other factors such as the subject's

underlying medical condition, concomitant therapy, or accident, and no temporal relationship exists between the study drug and the event.

Unlikely: The event does not follow a reasonable temporal sequence from drug

administration and is readily explained by the subject's clinical state or by

other modes of therapy administered to the subject.

Possibly Related: There is some temporal relationship between the event and the

administration of the study drug and the event is unlikely to be explained

by the subject's medical condition, other therapies, or accident.

Probably The event follows a reasonable temporal sequence from drug

Related: administration, abates upon discontinuation of the drug, and cannot be

reasonably explained by the known characteristics of the subject's clinical

state.

Related:

Definitely The event follows a reasonable temporal sequence from administration of

the medication, follows a known or suspected response pattern to the

medication, is confirmed by improvement upon stopping the medication (dechallenge), and reappears upon repeated exposure (rechallenge, if

rechallenge is medically appropriate).

11.1.5. Reporting Serious Adverse Events

Any SAE must be reported by phone or email to the Sponsor medical monitor and in writing via email or fax using the SAE report form within 24 hours of the Investigator's awareness of the SAE. In addition, all SAEs must be recorded on the AE CRF in real time.

All additional follow-up evaluations of the SAE must be reported to BioCryst or its designee as soon as they are available.

The SAE report forms should be sent to the following email addresses or fax numbers:

Email: [contact] and [contact]

OR

[contact] and [contact]

Immediate reporting should allow BioCryst to take the appropriate measures to address potential new risks in a clinical trial. Therefore, the initial report should be submitted by the Investigator within a very short period of time and under no circumstances should this period exceed 24 hours following awareness of the SAE.

The follow-up report should allow BioCryst to determine whether the serious adverse event requires a reassessment of the benefit-risk profile of the study drug in clinical trial, if the relevant information was not already available and provided in the initial report.

Any SAEs considered possibly, probably or definitely related to treatment and not in accordance with information in the Investigator's Brochure will be reported to the FDA and other Regulatory Competent Authorities as applicable via the MedWatch / CIOMS reporting system in accordance with FDA and other applicable regulations.

The Principal Investigator or designee at each site is responsible for submitting the IND safety report (initial and follow-up) or other safety information (e.g., revised Investigator's Brochure) to the Institutional Review Board (IRB) and for retaining a copy in their files.

11.1.6. Pregnancy

Pregnancy is not considered an AE but any pregnancy discovered in a subject during the course of the trial must be reported to BioCryst or designee on a pregnancy report form (supplied by BioCryst) in the same manner as SAEs (see Section 11.1.5). All pregnancies will be followed to an outcome (i.e. miscarriage, elective termination, stillbirth, live birth). Pregnancy outcomes of miscarriage, elective termination, stillbirth or birth defect will be considered SAEs and should be reported as per 11.1.5.

11.1.7. Reporting DAIDS Grade 3 or 4 events

Any DAIDS Grade 3 and Grade 4 clinical AE or laboratory abnormality that is judged to be possibly, probably, or definitely related to study treatment but does not meet seriousness criteria will be promptly (within 72 hours) reported to the study medical monitor via telephone or email.

11.2. Clinical Laboratory Evaluations

For any subject that is hospitalized, clinical chemistry, hematology and urinalysis samples will be analyzed by the local laboratory. Duplicate samples will not be drawn for analysis by the central laboratory.

11.2.1. Clinical Chemistry Profiles

Clinical chemistry profiles will include a Chemistry 20 panel (includes sodium, potassium, chloride, total CO₂ [bicarbonate], creatinine, glucose, urea nitrogen, albumin, total calcium, total magnesium, phosphorus, alkaline phosphatase, alanine aminotransferase (ALT), aspartate aminotransferase (AST), total bilirubin, direct bilirubin, lactate dehydrogenase (LDH), total protein, total creatine kinase, and uric acid).

Blood samples for clinical chemistry profiles will be collected at Baseline and at the Day 7 follow-up assessment. Clinically significant results should be reported as AEs.

11.2.2. Hematology Profiles

Hematology profiles will include complete blood count (CBC) with differential.

Blood samples for hematology profiles will be collected at Baseline, and at the Day 7 follow-up assessment. Clinically significant results should be reported as AEs.

11.2.3. Urinalysis

Routine urinalysis evaluations will include dipstick evaluations for protein, glucose, ketones, hemoglobin, and specific gravity. If indicated by dipstick results, the urine should be sent for microscopy.

Urinalysis will be conducted on urine samples obtained at Baseline, and at the Day 7 follow-up assessment. Clinically significant results should be reported as AEs.

11.2.4. Pregnancy Test (Urine or Serum)

Females of childbearing potential will be evaluated for pregnancy at Screening/Baseline and at the Day 7 follow-up assessment using a urine pregnancy test performed locally.

11.3. Vital Signs

Vital sign measurements (blood pressure (in children < 2 only if clinically indicated), heart rate, respiration rate, temperature) will be recorded once at Baseline and once at each follow-up visit.

11.4. Physical Examination and Influenza-Related Complications Assessment

The Investigator will perform a full physical examination at Baseline, including the subject's height or length and weight. At each follow-up visit, study personnel will evaluate the subject for the presence of clinical signs and/or symptoms of the following influenza-related complications: sinusitis, otitis media, bronchitis and pneumonia.

If the Investigator determines that the subject has (or is presumed to have) one of the influenza-related complications noted above, he/she will note that in the subject's source documents and on the influenza-related complications CRF page. Any medication used to treat the condition must also be recorded (on the concomitant medication page). The Investigator will promptly provide appropriate treatment for any suspected or proven influenza-related complication(s). Signs and symptoms associated with influenza-related complications will not be reported on the adverse event CRF page unless they meet criteria for an SAE.

11.5. Safety Oversight

Since the study is open label, a sponsor-led Data Safety Management Committee (DSMC) will oversee safety. A full review and summary of safety utilizing all collected safety assessments will occur after each influenza season. This will be described in the separate DSMC charter.

12. PHARMACOKINETIC ASSESSMENTS

For subjects randomized to peramivir, up to 4 plasma samples will be drawn for determination of drug concentration. The samples will be drawn, where possible, during the following time periods, beginning from the end of dosing:

- 1. One time point immediately following completion of the infusion
- 2. One time point from 30 minutes to 1 hours post-infusion
- 3. One time point from 1 hour to 3 hours post-infusion
- 4. One time point from 4 hours to 6 hours post-infusion

Plasma samples will be processed and shipped for analysis in accordance with instructions provided in the Laboratory Manual.

Note: Subjects ≥ 5 kg will have four 1.0 mL blood draws at the above stated sampling times. Subjects ≤ 5 kg will have two 1.0 mL blood samples; one time immediately following completion of the infusion and one time between 1-3 hours post-infusion.

13. STATISTICS

Descriptive statistical methods will be used to summarize the data from this study. Data will be summarized by treatment group, age group, and study day/time, if appropriate. Unless stated otherwise, the term "descriptive statistics" refers to number of subjects (n), mean, median, standard deviation (SD), minimum, and maximum for continuous data and frequencies and percentages for categorical data. The term "treatment group" refers to treatment assignment: single dose peramivir IV or oseltamivir BID for 5 days. The term "age group" refers to the following: 0-28 days; 28 days -<2 years, ≥ 2 years -<7 years, ≥ 7 years -<13 years, and ≥ 13 years -<18 years. All data collected during the study will be included in data listings. Unless otherwise noted, the data will be sorted first by treatment group, age group, subject number, and then by date within each subject number.

The statistical analyses will be conducted with the SAS® software package version 9.2 or higher. All analyses will be subject to formal verification procedures. Specifically, results will be verified utilizing independent programming prior to issuance of the draft statistical report. All documents will be verified by the lead statistician to ensure accuracy and consistency of analyses.

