- 5. Females who are pregnant (positive urine or serum pregnancy test) or breast-feeding at screening.
- 6. Onset of symptoms more than 72 hours before presentation for screening for subjects <2 years old.
- 7. Development of symptoms while hospitalized for another indication
- 8. Subjects with identified risk factors for influenza complications but with uncomplicated influenza at the time of enrollment are not excluded. This includes lung disease, heart disease, blood disorders such as sickle cell anemia, metabolic disorders and neurologic disease. In addition, mild to moderate immunocompromised status such as due to renal disease, diabetes mellitus or HIV infection with a last known CD4+ count ≥200 cells/µl are not excluded.
- 9. Presence of severe immunocompromised status due to chronic disease or illness, previous organ transplant, or use of immunosuppressive medical therapy which would include oral or systemic treatment with > 10 mg prednisone or equivalent on a daily basis within 30 days of screening.
- 10. Complicated influenza characterized by any of the following:
 - a. ICU care
 - b. Evidence of organ dysfunction
 - c. Proven or suspected concomitant bacterial infection
 - d. Other known concomitant viral infection that is likely to complicate medical course such as RSV, parainfluenza virus and adenovirus. Co-infection with rhinovirus and enterovirus is allowed.
- 11. Previous participation in Study BCX1812-305 or participation in a study of any investigational drug or device within the last 30 days.
- 12. Subjects who cannot comply with all aspects of the study protocol.

Investigational product, dosage and mode of administration:

Subjects assigned to receive peramivir, will receive an age-appropriate single dose of peramivir, diluted appropriately in normal saline, administered as a short intravenous infusion over a minimum of 15 minutes.

- Subjects ≥ 13 years will receive a dose of 600 mg.
- Subjects ≥ 6 months to ≤ 12 years will receive a dose of 12mg/kg (to a maximum dose of 600 mg).
- Subjects < 6 months will receive a dose of 8mg/kg.

Reference therapy, dosage and mode of administration:

Subjects randomized to oral oseltamivir will receive an age appropriate dose twice daily for 5 days.

- Subjects ≥ 13 years will receive a 75mg dose administered as a capsule or oral suspension (twice daily for 5 days).

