- Subjects 28 days to < 13 years of age will receive a weight-based dose administered as a capsule or oral suspension (twice daily for 5 days).

Note, as of the approval of amendment 3, no additional subjects will be randomized to receive oseltamivir.

Criteria for evaluation:

Safety:

• Safety will be evaluated through assessments of Adverse Events (AEs), laboratory analyses (clinical chemistry, hematology and urinalysis), vital signs, and physical examinations. A review and summary of safety utilizing all collected assessments will be performed by a Data Safety Monitoring Committee (DSMC) after each influenza season as outlined in the DSMC charter.

Pharmacokinetic:

• Plasma peramivir concentrations will be measured by a validated liquid chromatography-tandem mass spectrometry (LC/MS-MS) assay. Concentrations will be utilized in determination of population pharmacokinetic parameters.

Effectiveness:

- **Clinical:** Time to resolution of fever; time to resolution of influenza symptoms (per the age appropriate symptoms);
- **Virologic:** Viral shedding; virus susceptibility.

Statistical methods:

Sample Size:

The study is designed to evaluate the safety and pharmacokinetics of IV administration of peramivir in pediatric subjects with influenza. The sample size is adequate to evaluate these objectives. Descriptive comparison between peramivir and oseltamivir treated subjects will be performed where possible. Formal hypothesis testing will not be performed.

Safety:

Qualitative analyses will be performed for AE type, frequency and severity, as well as vital sign absolute values, clinical laboratory absolute values, and physical examination findings and their respective changes from Baseline for all subjects.

Pharmacokinetics:

Plasma concentrations and covariates of interest will be evaluated in a meta-population analysis using mixed effect modeling techniques to estimate population pharmacokinetic parameters in each age group and to identify pharmacokinetically-relevant covariates. Data from the completed pediatric study 0918T0633 of IV peramivir in Japan will be included in this analysis.

Effectiveness:

Clinical and virologic endpoints will be summarized using descriptive statistics.

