5.4. Rationale for Study

There remains a significant unmet need for influenza therapies in children. Currently, the only available options are oral or inhalation, both of which have limitations, both in terms of administration and viral resistance. Peramivir has demonstrated efficacy and safety when used in acute uncomplicated influenza in adults. However, there is significant clinical and real world experience with pediatric use indicating that there is both efficacy and safety when used in healthy and high-risk children as young as 28 days. Most children treated to date have been Asian, so the current study will provide valuable information in other racial and ethnic groups.

Because children bear a larger burden of infection during seasonal influenza and are at greater risk for complications during pandemics, new treatments for children are needed. During the last pandemic of 2009-2010, the rates of hospitalization, admission to intensive care units, and invasive life support were higher than for past seasonal influenza with the highest proportion of seriously ill patients being children and young adults (Dominguez-Cherit, Lapinsky et al. 2009,

Jain, Kamimoto et al. 2009, WHO 2009). The approved dose of peramivir in adults is a single dose of 600 mg because of improved efficacy without an increase in safety risk. Population pharmacokinetic modeling performed by the FDA (July 2009) based on the Shionogi Studies 0816T0633 (children and adolescents) and 0722T0621 (adults) supports a target dose of 12 mg/kg/day in children (6 to 12 years) to attain exposures similar to that in adults who receive a 600 mg IV dose.

In order to provide recommendations for dosing in subjects less than 6 months of age, an updated population PK model was developed that included all available data from adult and pediatric studies, and data from an interim review of BCX1812-305. Simulations from this model indicate that a dose of 8 mg/kg/day in children from birth to < 6 months of age should provide exposure of peramivir similar to that observed in adult subjects and pediatric subjects who have completed BCX1812-305. In subjects 6 month of age and older, a 12 mg/kg dose is simulated to attain exposures in pediatric subjects similar to that in adults administered a 600 mg IV dose. Simulations indicate that in subjects < 6 months of age, the predicted exposure following an 8 mg/kg dose will not exceed that of adults.

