9.2. Treatments Administered

9.2.1. Peramivir

Peramivir solution for infusion is a clear, iso-osmotic, sterile, nonpyrogenic solution in 200 mg per 20 mL (10 mg/mL) single-use glass vials fitted with rubber stoppers and aluminum flip-off seals. The drug product should be stored at room temperatures up to 30°C.

Subjects < 6 months of age at time of consent will receive a single dose of IV peramivir at a dose of 8 mg/kg. Subjects ≥ 6 months $- \le 12$ years of age at time of consent will receive a single dose of IV peramivir at a dose of 12 mg/kg (up to a maximum dose of 600 mg). Subjects ≥ 13 years of age will receive a single dose of 600 mg IV peramivir administered as a short IV infusion over a minimum of 15 minutes. Peramivir must be diluted in normal saline normal saline United States Pharmacopeia (SUP).:

Because of the risk of vasovagal reactions, particularly in children with needle phobia, it is recommended that subjects be in a supine position during peramivir administration. Appropriate post infusion observation should be performed.

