#### 2.1. STUDY OVERVIEW

Protocol BCX1812-305 is a multicenter, randomized, open-label, active-controlled study to evaluate the safety, pharmacokinetics and effectiveness of a single dose of intravenous (IV) peramivir (600 mg IV or 12 mg/kg IV depending on age) compared to oral oseltamivir (dosed BID for 5 days) in children with uncomplicated acute influenza. Approximately 140 subjects will be enrolled. Up to 10 subjects ages from birth to <– 28- days will be enrolled and will receive a single dose of intravenous (IV) peramivir 12 mg/kg. Up to 20 subjects 28 days to less than 2 years old will be enrolled. Subjects enrolled in this cohort prior to version 4.0 of the protocol will be randomized 4:1 (4 IV peramivir: 1 oral oseltamivir) whereas subjects enrolling in this cohort under version 4.0 or higher of the protocol will receive IV peramivir 12mg/kg. Up to 110 subjects 2 years to < 18 years of age will be randomized 4:1 (4 IV peramivir: 1 oral oseltamivir) according to the following age groups:

- 2 years < 7 years: up to 40 subjects
- 7 years < 13 years: up to 40 subjects
- 13 years < 18 years: up to 30 subjects

Eligible subjects with have clinical signs and symptoms consistent with acute influenza infection consisting of an oral temperature  $\geq 100^{\circ}F$  or rectal temperature  $\geq 101.3^{\circ}F$  with at least one respiratory symptom (cough or rhinitis) OR a positive influenza rapid antigen test (RAT). Enrollment of eligible subjects based on clinical symptoms alone will be approved by the Sponsor at the beginning of each influenza season.

The formulation of the peramivir drug to be used in this study contains peramivir at a concentration of 10 mg/mL. The peramivir 10 mg/mL stock solution will be diluted in saline using aseptic techniques with a maximum volume of 100 mL. Oseltamivir will be prepared and administered in accordance with the manufacturer's instructions.

Subjects will record temperature, influenza symptoms, date and time of oral oseltamivir dose administration (if applicable), the ability to return to day care/school and/or resume their normal daily activities, appetite and eating patterns, and doses of symptomatic relief medication in a Subject Diary. Temperature measurements will be taken every 12 hours until temperature

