# **6.2.3.** Exploratory Exposure Response Analyses

Summaries of plasma concentrations will be presented by time point, age group, and treatment group. Scatter plots will be generated for time to alleviation of influenza symptoms and change from baseline in  $\log_{10} \text{ TCID}_{50}/\text{mL}$  versus peramivir plasma concentration at 30-60 minutes following study drug administration. The data from this trial together with data from prior trials will be used to complete a separate exposure-response analysis. The methods for the exposure-response analysis will be presented in a separate SAP.

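### No planned summary table separates the 8 mg/kg and 12 mg/kg peramivir doses within the 28 days to <2 years group

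*Protocol*

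**What the plan says.** Protocol 9.2.1 sets the lower dose step: "Subjects < 6 months of age at time of consent will receive a single dose of IV peramivir at a dose of 8 mg/kg". The Synopsis gives the next band: "Subjects ≥ 6 months to ≤ 12 years will receive a dose of 12mg/kg", capped at 600 mg.

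Protocol 13 defines the reporting groups. Age group "refers to the following: 0-28 days; 28 days -<2 years, ≥ 2 years -<7 years", followed by two older bands. Treatment group "refers to treatment assignment: single dose peramivir IV or oseltamivir BID for 5 days". Protocol 13.7.3 adds viral subtype as the only other planned breakdown. SAP section 6 uses the same 28 days to <2 years band and lists no neonatal band.

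The displays follow these groups:
- SAP 6.2.3, concentrations: "Summaries of plasma concentrations will be presented by time point, age group, and treatment group".
- SAP 6.3.3 and 6.3.4, laboratory results and vital signs: by visit and treatment group, for each age group and overall.
- Protocol 13.9, treatment-emergent adverse events: by age group and treatment group. SAP 6.3.1 gives the same events by treatment group only.

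Protocol 5.4 supports the infant dose by simulation, stating for those under 6 months that "the predicted exposure following an 8 mg/kg dose will not exceed that of adults". SAP 2.1 says of the 28 days to <2 years cohort that "subjects enrolling in this cohort under version 4.0 or higher of the protocol will receive IV peramivir 12mg/kg". It gives the same mg/kg dose for neonates, and 8 mg/kg appears nowhere in the SAP.

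**The concern.** The other dose step, at 13 years, coincides with a boundary between analysis groups. The step at 6 months falls inside one. A row that mixes two mg/kg levels describes neither, and its result cannot be attributed to a dose from the table alone.

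This matters most for the younger infants. Their dose rests on a model prediction, and this trial supplies observed data against which to set it. Safety is the primary objective, yet no planned adverse event or laboratory table isolates infants of 28 days to <6 months given 8 mg/kg.

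**Working it through.** **1. The plan's own figures.** The age caps in protocol 7.2 sum to 10 + 20 + 10 + 30 + 40 + 30 = 140, as stated. Protocol 13.4 puts about 117 on peramivir. Taking both cohorts under 2 years as all peramivir and 4:1 for the other 110 gives 10 + 20 + 0.8 × 110 = 118, within one of that figure. Neither total says how many infants receive each dose, and the point does not depend on them.

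**2. Does a dose step fall inside the group?** Table 3 in protocol 9.4.1, at 10 mg/mL, gives mg/kg = 10 × volume ÷ weight.
- 28 days to <3 months: 10 × 2.4 ÷ 3 = 8.0 and 10 × 6.0 ÷ 7.5 = 8.0.
- 6 to <12 months, upper end: 10 × 13.4 ÷ 11.2 = 12.0.

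So two dose levels do occur within 28 days to <2 years. Two other entries do not match the stated doses: 3 to <6 months at the upper end, 10 × 4.7 ÷ 11.2 = 4.2, and 6 to <12 months at the lower end, 10 × 7.2 ÷ 4.5 = 16.0. The volumes, weight ranges and doses need reconciling. I take no view on which is right.

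**3. How many infants?** Not stated. Assume ages uniform from 28 days (0.92 months) to 24 months:

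(6 − 0.92) ÷ (24 − 0.92) = 22%, and 20 × 0.22 = 4.4, so about 4 of 20.

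The possible range is 0 to 20. SAP 2.1 has some of this cohort randomized to oseltamivir under earlier protocol versions, so the peramivir total may be below 20.

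**4. What can a pooled concentration row show?** Suppose k of 20 infants are below 6 months and their mean exposure is g times that of the rest (g is assumed, for illustration). The pooled mean, relative to the older infants, is (k·g + 20 − k) ÷ 20.

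| k | g = 1.5 | g = 2 |
|---|---|---|
| 2 | 1.05 | 1.10 |
| 4 | 1.10 | 1.20 |
| 10 | 1.25 | 1.50 |

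With k = 4, a doubling in the younger infants moves the pooled mean by only 20%. The row can neither confirm nor refute the statement about 8 mg/kg.

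**5. What can a pooled safety row show?** With zero events in n subjects, the exact one-sided 95% upper bound on the event rate is 1 − 0.05^(1/n). For n = 20 it is 13.9%; for n = 4 it is 52.7%. The pooled row does not show how little of its evidence comes from the lower dose.

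**The case against.** There are other routes to the 8 mg/kg question, and they count.
- **Neonates.** Under the current protocol the birth to <28 days cohort (up to 10) receives 8 mg/kg only, and protocol 13 gives it its own group. This is partial evidence. Protocol 9.1 models renal maturation up to age 2, so neonates do not simply stand in for infants of 1 to 6 months, and the SAP's age-group list omits them.
- **Population PK.** The Synopsis plans a mixed-effects analysis with covariates, which can use each infant's own dose and age. This is the strongest answer on exposure. Its results are nonetheless described as intended "to estimate population pharmacokinetic parameters in each age group", and it does nothing for the safety tables.
- **Listings.** Dosing, concentrations and adverse events are listed by subject. For about four infants a listing conveys much of what a column would. However, SAP section 9 restricts listings to randomized subjects, while SAP section 5 promises all enrolled. That is a separate inconsistency, but it weakens this route for infants assigned without randomization.

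The SAP also looks older than the dose step: a page footer reads 11 July 2016, it cites protocol version 4.0, and the current protocol is version 6.0. SAP 6.2.3 need not be a deliberate choice to pool. That does not dispose of the point, because section 13 of the current protocol has the same unbroken band.

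Finally, mg/kg varies within other groups too, through the 600 mg cap and the flat dose from 13 years, and a column of four is thin. Both are true. In a descriptive study with no hypothesis tests, a small labelled column costs no power.

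**Conclusion.** The point holds as a gap in the summary tables: within 28 days to <2 years none separates the two peramivir doses. Those tables cannot on their own show exposure or safety at 8 mg/kg between 28 days and 6 months. For exposure the gap is partly covered elsewhere; for safety in that age range only the listings remain. The extent is unknown: about 4 of 20 under uniform ages, 0 to 20 in principle. It is a cheap improvement, not a flaw in the design.

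Three stronger readings are not supported:
- A reader might infer that the trial cannot check the 8 mg/kg dose at all. The neonatal group and the population PK model both bear on it.
- A reader might infer that every display is by age group and treatment group. SAP 6.3.1 uses treatment group alone for adverse events, and effectiveness is also shown by viral subtype.
- A reader might compute a fixed percentage bias in the pooled mean from the ratio of 8 to 12. That needs concentration proportional to mg/kg and a known age mix. The protocol's premise is instead that the lower dose gives similar exposure, and the age mix is not given.

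Whether any infant under 6 months received 12 mg/kg under an earlier protocol version is also inference. It is the reason to tabulate by dose received as well as by age.

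**What to change.** In protocol 13 and SAP section 6, present peramivir subjects in this group by mg/kg dose actually received, with a cut at 6 months (28 days to <6 months; 6 months to <2 years). Base the cut on age at consent, which protocol 9.2.1 uses for dosing; SAP 4.3.8 defines age at randomization, which does not exist for infants assigned directly. Keep the combined column as secondary.

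Apply this to Tables 14.4.1.1, 14.4.1.2, 14.3.5.x and 14.3.6. Apply it to Tables 14.3.1.x once the adverse event summary by age group that protocol 13.9 requires has been restored in SAP 6.3.1.

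Reconcile the 12 mg/kg that SAP 2.1 states for the youngest cohorts with the protocol's 8 mg/kg below 6 months. This review does not say which is right.

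The cost is SAP and protocol wording and one or two extra columns, from dose and age data already collected. The drawback is small cells in the youngest columns, which should be shown with their counts and not over-read.
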